1. INTRODUCTION AND STUDY RATIONALE

1.1. HIV Infection

1.1.1. Disease

1.1.2. Management of subjects

1.2. ABX464 rationale

1.2.1. Investigational treatment description

1.2.2. Investigational product description

1.2.3. Investigational product mode of action

1.2.4. Rationale for the development of ABX464

1.2.5. Preclinical data of ABX464

1.2.5.1. Non-clinical background information

1.2.6. Previous clinical experience with ABX464

1.3. Rationale for the clinical study and study design

1.3.1.

2. STUDY OBJECTIVES

2.1. Primary Objective

- To evaluate the distribution of ABX464 and its main metabolite (ABX464-N-glucuronide) in various compartments in HIV-1 Seronegative and Seropositive adult subjects.

2.2. Secondary Objective

- To evaluate the safety of ABX464 administered once daily at one dose, alone in HIV-uninfected subjects and in combination with ARTs in HIV-1 infected adult subjects;
- To evaluate the systemic and mucosal immunological response to ABX464 in HIV-uninfected and or in HIV-infected adult subjects;
- To evaluate the effect of ABX464 on the HIV reservoir cells in HIV-infected adult subjects;
- To evaluate the effect of ABX464 on the control of the viral load and the CD4+/CD8+ in HIV-infected adult subjects;
- To evaluate the effect of ABX464 on the microbiome in HIV-1 Seronegative and Seropositive adult subjects;
- To evaluate the effect of ABX464 on the rectal transcriptome & proteome in HIV-1 Seronegative and Seropositive adult subjects.

3. INVESTIGATIONAL PLAN

3.1. Study design

3.1.1. Design and methodology

The ABX464-005 study is a Phase Ib, sequential cohort open label trial designed to provide additional safety and compartmental PK data on ABX464.

The study will also generate exploratory immunological and virological data that combined with the compartmental PK data will help further characterize the mechanism of action of ABX464.

The study will enroll both HIV-infected (N=24) and HIV-uninfected (N=12) study subjects in three distinct cohorts:

- Cohort 1: 12 HIV-infected subjects treated with ABX464 150 mg o.d. for 28 days
- Cohort 2: 12 HIV-uninfected subjects treated with ABX464 50 mg o.d. for 28 days
- Cohort 3: 12 HIV-infected subjects treated with ABX464 50 mg o.d. for 84 days

HIV-infected subjects will add the investigational product to their current antiretroviral regimen whereas the HIV-uninfected subjects will only receive the investigational product.

Cohort 1 will consist of 12 HIV infected subjects. After full enrollment and an interim analysis (including PK and immunological markers) of Cohort 1, Cohort 2 and 3 will begin enrollment and will consist of both HIV infected (n=12) and HIV uninfected (n=12) subjects.

Subjects who successfully complete a screening visit (Visit 1) will advance to a Baseline visit (Visit 2; Day 1). During this visit all subjects will undergo a physical examination and have blood and rectal tissue samples collected.

The rectal tissue samples will be collected before initiating oral dosing with the investigational product (150 mg or 50 mg of ABX464).

After receiving the first dose of ABX464, additional blood PK samples will be collected at 0h, 0.5h, 1h, 1.5h, 2h, 4h, 6h and 8 hours.

All subjects will receive the investigational product once daily for 28 days (Cohorts 1 &2) and for 84 days (Cohort 3).

At Day 28 for subjects enrolled in cohort 3 and at the end of the treatment period (End of Rx Visit; Day 28 for Cohorts 1&2 and Day 84 for Cohort 3) subjects will undergo a physical examination and have blood and rectal tissue collected. PK blood samples will be collected at 0h, 0.5h, 1h, 1.5h, 2h, 4h, 6h and 8 hours.

HIV infected subjects will continue with their antiretroviral regimen i.e. there will be no antiretroviral treatment interruption in this study.

Additional follow-up visit will occur 1 week (Day 35 / Day 91) and 1 month (End of study visit; Day 56 / Day 112) after stopping study product. During these two visits the subjects will undergo a physical examination and have blood (through PK) and rectal tissue samples collected at End of Study (EoS) visit only (Rectal tissue only for Cohorts 1 and 3).

The blood samples collected in this study will be used to characterize general safety, and in HIV infected subjects to monitor viral load and CD4+ counts, to quantify PK exposure to ABX464 and its metabolites, and blood samples collected will be used to assess systemic immunological effect of ABX464 and alteration of HIV reservoir.

Rectal biopsies will be collected 15 cm from the anal verge and will be used to quantify PK exposure in rectal tissue, to determine whether ABX464 alters gut associated lymphoid tissue (GALT) immunology, and to assess whether exposure to ABX464 alters HIV GALT reservoirs in the HIV-infected subjects or reduce the incidence or magnitude of HIV infection in rectal tissue from HIV-uninfected subjects. GALT HIV reservoirs (RNA and DNA) will be characterized using previously published techniques (4). Ex vivo / in vitro rectal explant challenge will also be performed using previously published techniques in which rectal biopsies are challenged with high titers of HIV-1_{BAL} and cumulative, weight adjusted HIV-1 p24 antigen is quantified in the explant supernatant (2). Additional studies of mucosal proteome, transcriptome, and microbiome will provide a comprehensive assessment of mucosal biology before and after exposure to ABX464.

The ABX464-005 study design is summarized below.

3.1.2. Dose limiting toxicity (DLT)

A dose limiting toxicity (DLT) is defined as a grade 3 or higher adverse event as defined by the Division of AIDS Toxicity Table for Severe Adult and Pediatric Adverse Events (including signs/symptoms, lab toxicities and/or clinical events) considered by a safety review board as probably or definitely related to study treatment. The first four subjects will be enrolled first and followed up for at least 2 weeks of treatment. If more than 2 DLTs occur of the first four treated subjects during ongoing study participation, then the enrolment of additional subjects will be stopped.

In addition, in case of a life threatening (grade 4) adverse reaction enrolment and treatment of ongoing subjects will be immediately discontinued.

In both cases, enrolment will only be resumed upon the decision of the sponsor if the Data Safety Monitoring Board can conclude that the causality of the event was unrelated or unlikely related to study treatment.

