GGT	gamma-glutamyl transferase
GM	geometric mean
H	hours
HAART	Highly Active Anti-Retroviral Therapy
HIV	Human Immunodeficiency Virus
HR	heart rate
IB	Investigator's Brochure
ICF	informed consent form
ICH	International Conference on Harmonisation
IMP	Investigational Medicinal Product
IEC	Independent Ethics Committee
Max	maximum
MedDRA	Medical Dictionary for Regulatory Activities
mg	milligram
Min	minimum
mL	milliliter
mmHg	millimeters of mercury
NOAEL	No Observed Adverse Effect Level
o.d.	Once Daily
PD	pharmacodynamics
PK	pharmacokinetics
PT	preferred term
PCSA	potentially clinically significant abnormalities
QTc	heart-rate-corrected QT interval (time between the start of the Q wave and the end of the T wave in the heart's electrical cycle) using Bazett's formula
R	Accumulation ratio
RTV	Ritonavir
Rx	Treatment
SAE	serious adverse event
SBP	systolic blood pressure
SD	standard deviation
SEM	standard error of the mean
SOC	system organ class
TEAE	treatment emergent adverse event
t _{lag}	interval between administration time and the sampling time preceding the first concentration above the limit of quantification
t _{1/2}	terminal half-life
t _{max}	time to peak plasma concentration
Vd/F	volume of distribution
vs.	versus

SYNOPSIS

Study n°	ABX464-005	Clinical Phase	Ib
		Type of Study	PK/Safety Study
Study title	An Open-Label Study of the Safety, Pharmacokinetics, and Pharmacodynamics of ABX464 in HIV-1 Seronegative and Seropositive Adults		
Short title	Safety study of ABX464 in HIV-1 Seronegative and Seropositive adult subjects.		
Investigators and study centers	
The study will be conducted at the Hospital Universitari Germans Trias i Pujol (Can Ruti), Badalona, Spain
 
Collaborating centre: BCN Checkpoint, Barcelona, Spain
		
Study Duration	
Recruitment period: Q4 2016 – Q2 2018
 
Overall Study period: Q4 2016 – Q1 2019
		
Investigational product			

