Study Methodology	
The purpose of the ABX464-005 study is to characterize the systemic and mucosal immunological sequelae associated with exposure to ABX464 and to explore selected immunological endpoints, compartmental pharmacokinetics, and pharmacodynamics. The site will screen and enroll 12 HIV-infected subjects who will receive 150 mg ABX464 orally once daily for 28 days (Cohort 1). Following completion of this cohort a further 24 subjects will be enrolled: 12 HIV-uninfected subjects will receive 50 mg ABX464 orally once daily for 28 days (Cohort 2) and 12 HIV-infected subjects (Cohort 3) who will 50 mg ABX464 orally once daily for 84 days.
 
Following screening, eligible subjects in all cohorts will undergo a baseline visit during which blood and tissue samples will be collected. All subjects will have additional blood and tissue samples collected on Day 28 of dosing (and on Day 84 for subjects enrolled in cohort 3) and four weeks after completion of dosing (excluding cohort 2 for tissue samples). The HIV infected subjects should be receiving a stable combination antiretroviral regimen for 12 months and be fully virally suppressed (plasma viral load < 50 copies/mL) during the last 6 months prior to enrolment.
 
Dose limiting toxicity (DLT) is defined as a grade 3 or higher adverse event as defined by the Division of AIDS table for grading the severity of adult and pediatric adverse events (including signs/symptoms, lab toxicities and/or clinical events) considered by the Data Safety Monitoring Board as probably or definitely related to study treatment.
 
If more than 2 DLTs occur during the treatment period of the first four treated subjects, then the enrolment of additional subjects will be stopped. In addition, in case of a life threatening (grade 4) adverse reaction enrolment and treatment of ongoing subjects will be immediately discontinued. In both cases, enrolment will only be resumed upon the decision of the sponsor if the Data Safety Monitoring Board can conclude that the causality of the event was unrelated or unlikely related to study treatment.
		
Study Design			

Study n°	ABX464-005	Clinical Phase	Ib
		Type of Study	PK/Safety Study

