5. STUDY ASSESSMENTS AND PROCEDURES

5.1. Study Flow Chart

A detailed study flow chart (with all assessments) is displayed below.

Study procedures	Screening Visit	Baseline Visit	Control Visits	Day 28 / D56	End of Study treatment visit	FU visit	FuS visit Cohort 1&3	FuS visit Cohort 2
	Screening 21 ± 7 days	Baseline	Cohort 2 only ± 2 days	Cohort 3 only ± 2 days	28-Day (Cohort 1&2), 84-Day (Cohort 3) ± 2 days	FU visit 1-week post completion ± 2 days	FU visit 4 weeks post completion ± 7 days	FU visit 4 weeks post completion ± 7 days
Informed Consent	X	Day 1	Day 7, 14, 21	Day 28 / D56	Day 28 / Day 84	Day 35 / Day 91	Day 56 / Day 112	Day 56
Inclusion/Exclusion Criteria	X							
ECG	X	X			X		X	X
Adverse Event reporting	X	X	X	X	X	X	X	X
Concomitant medication checks and	X	X	X	X	X	X	X	X
Physical examination and vital signs	X	X	X	X	X	X	X	X
Hematology & Biochemistry	X	X						
Syphilis, HBV/HCV serology	X							
HIV-1 antibody serology #	X							
Urine and Rectal GC/CT (NAAT)	X				X	X	X	X
TNR & PT	X	Δ			Δ	Δ	Δ	Δ
HIV-1 viral load \$	X	X			X*	X	X	X
CD4+ and CD8+ counts \$	X	X			X*	X	X	X
Pharmacokinetics: Plasma and PBMC		0h, 0.5h, 1h, 1.5h, 2h, 4h, 6h and 8h	X*	X*	0h, 0.5h, 1h, 1.5h, 2h, 4h, 6h and 8h	X Trough	X Trough	X Trough
Flexible sigmoidoscopy for Rectal Biopsy		X			X*	X	X	X
- Explant infection #	X				X*	X	X	X
- MMC flow cytometry	X				X*	X	X	X
- Rectal microbiome	X				X*	X	X	X
- Rectal proteomics	X				X*	X	X	X
- Rectal transcriptomics	X				X*	X	X	X
- Rectal tissue pharmacokinetics	X				X*	X	X	X
- Rectal HIV Reservoir \$	X				X*	X	X	X
Blood samples for Immunology & Molecular assays		X			X*	X	X	X
- PBMC flow cytometry	X				X*	X	X	X
- Plasma SCAs \$	X				X*	X	X	X
- Plasma inflammatory markers	X				X*	X	X	X
Blood samples for HIV reservoir assays \$		X			X	X	X	X
- PBMC HIV reservoir \$	X				X	X	X	X

CT; Chlamydia trachomatis, GC; Neisseria gonorrhoea, HBV; hepatitis B virus, HCV; hepatitis C virus, INR; international normalized ratio, NAAT; nucleic acid amplification testing, MMC; mucosal mononuclear

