5.3.2. Baseline Visit (Day 1)

- Physical examination and vital signs;
- Microbiome specimen collection (swabs);
- Hematology (incl. INR and PT if clinically indicated);
- Biochemistry;
- 12 lead ECG;
- Viral Load, CD4/CD8 count (HIV infected Subjects);
- Blood collection for HIV reservoir assessment (HIV infected Subjects) and immuno-evaluation;
- Flexible sigmoidoscopy with collection of rectal biopsies;
- Dispense study treatment to subject and instruct how to take them
- Perform PK blood samples (0h, 0.5h, 1h, 1.5h, 2h, 4h, 6h and 8 hours);
- Adverse event assessment.

5.3.3. Control Visits 3,4, & 5 (Days 7, 14, & 21)- Cohort 2

To be performed only in HIV-uninfected subjects:

- Physical examination and vital signs;
- Check Study treatment compliance;
- Adverse event assessment.

5.3.4. Day 28 Visit (\pm 2 days)- Cohort 3

To be performed only in subjects enrolled in the Cohort 3:

- Physical examination and vital signs;
- Microbiome specimen collection (swabs);
- Hematology (incl. INR and PT if clinically indicated);
- Biochemistry;
- Viral Load, CD4/CD8 count;
- Blood collection for HIV reservoir assessment and immuno-evaluation;
- Flexible sigmoidoscopy with collection of rectal biopsies;
- Perform PK blood samples (0h, 0.5h, 1h, 1.5h, 2h, 4h, 6h and 8 hours);
- Check Study treatment compliance;
- Adverse event assessment.

5.3.5. Day 56 Visit (\pm 2 days)- Cohort 3

To be performed only in subjects enrolled in the Cohort 3:

- Physical examination and vital signs;
- Hematology and Biochemistry;

- Blood collection for HIV reservoir assessment and immuno-evaluation;
- Check Study treatment compliance;
- Adverse event assessment.

5.3.6. End of study treatment visit (D28 for cohort 1&2 or D84 for cohort 3; \pm 2 days)

- Physical examination and vital signs;
- Microbiome specimen collection (swabs);
- Hematology (incl. INR and PT if clinically indicated);
- Biochemistry;
- 12 lead ECG;
- Viral Load, CD4/CD8 count (HIV infected Subjects);
- Blood collection for HIV reservoir assessment (HIV infected Subjects) and immuno-evaluation;
- Flexible sigmoidoscopy with collection of rectal biopsies;
- Perform PK blood samples (0h, 0.5h, 1h, 1.5h, 2h, 4h, 6h and 8 hours);
- Check Study treatment compliance;
- Adverse event assessment.

5.3.7. Follow-up Visit (D35 for cohort 1&2 or D91 for cohort 3; \pm 2 days)

- Physical examination and vital signs;
- Hematology (incl. INR and PT if clinically indicated);
- Biochemistry;

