5.4.3. Hematology and biochemistry

For hematology and biochemistry local laboratories will be used. All laboratory results and reference ranges for safety parameters must be entered in the eCRF. Each laboratory value that is outside of the institution's normal range will be identified. The investigator will be responsible for assessing the clinical significance of laboratory abnormalities. If the investigator is uncertain about the clinical significance of a laboratory abnormality, he/she will consult with the Sponsor medical monitor. The investigator should follow any clinically significant laboratory abnormalities until resolution.

Table 4 displays the clinical laboratory parameters that must be measured at every visit.

Table 4: Laboratory Tests

HEMATOLOGY		BIOCHEMISTRY
Hemoglobin		Sodium
Hematocrit		Potassium
WBC		Chloride
Neutrophils		Calcium
Lymphocytes		Phosphate
Monocytes		Glucose
Eosinophils		BUN or urea
Basophils		Creatinine
Platelet count		AST
INR		ALT
PT		Alkaline phosphatase
		Total bilirubin
		GLDH
		Total protein
		Lipase
		Albumin
		LDH
		gGT
		CRP

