5.4.8. Pharmacokinetics

Plasma and tissue ABX464 and its metabolite concentrations will be determined by liquid chromatography tandem mass spectrometry (LC-MS/MS) methods validated for all matrices by ATLANBIO.

ABX464

After single oral administration of 50 to 200 mg ABX464, ABX464 is relatively quickly absorbed and undergoes a very extensive biotransformation into its N-glucuronide metabolite, NGlc.

In most of the subjects, regardless of the dose, ABX464 plasma concentration is generally not measured after 8 to 10 h post-dose. Cmax is generally observed within the first 2 h post-dose and then ABX464 plasma concentrations decreased with a $t_{1/2}$ of about 1 to 2 h.

ABX464-N-glucuronide's plasma concentrations were markedly higher than those of the parent drug with mean Cmax about 200 to 300-fold higher than ABX464 Cmax. Cmax was observed around 4 h post-dose with a very limited variability thereafter ABX464 NGlc was slowly eliminated and had a $t_{1/2}$ of 90 to 110 h.

Relationship between rate and extent of absorption of ABX464 and ABX464 dose is quite erratic with a reduced increase with the dose up to 150 mg and saturation like behavior at 200 mg.

ABX464-N-glucuronide's exposure-dose relationship is somehow comparable to that of ABX464 although increase of C_{max} and AUCs tend to be dose proportional between 50 and 150 mg.

Since ABX464 undergoes a high level of biotransformation, ratios between metabolite and parent drug appear to be unchanged across the studied dose range but inter-individual variability prevented from definite conclusions.

Therefore, ABX464 should rather be considered as a pro-drug with regard to its short $t_{1/2}$. Its metabolite, ABX464-N-glucuronide exhibits markedly higher blood concentrations and has a much longer $t_{1/2}$ which could be of pharmacological interest. Last, dose-exposure relationship appears erratic between 50 and 200 mg but tends to linearity up to 150 mg.

ABX464 was shown to have a very short $t_{1/2}$ (1 to 2 h), so steady-state is virtually reached at the second administration, while ABX464-N-glucuronide has a $t_{1/2}$ of 90 to 110 h, meaning that steady-state is reached after 19 to 22 days of administration. Intense PK blood collection is planned to be done on Day 1 (initiation of ABX464 administration) and Day 28 (final dose of ABX464) to characterize accumulation and decay of ABX464 and its metabolite (ABX464-N-glucuronide) in plasma and PBMC.

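### Cohort 1 has no scheduled safety lab between Day 1 and Day 28, so the 2-week hold on the first four subjects can end before all four are measured; for Cohort 2 the documents conflict on labs during dosing

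*Protocol*

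**What the plan says.** **The hold and the DLT rule.** Protocol 3.1.2 counts related events of grade 3 or above as DLTs, "including signs/symptoms, lab toxicities and/or clinical events". It sets the hold as follows: "The first four subjects will be enrolled first and followed up for at least 2 weeks of treatment". More than 2 DLTs in these four stops enrolment. The synopsis counts over a longer span: "If more than 2 DLTs occur during the treatment period of the first four treated subjects". Protocol 6.4 fills Cohort 1 first, so the four are Cohort 1 subjects on 150 mg.

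**Cohort 1 visits.** Protocol 5.3.3 restricts the Day 7, 14 and 21 visits: "To be performed only in HIV-uninfected subjects". SAP 3.4 agrees. After Day 1, Cohort 1 is next seen at Day 28 ± 2.

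**Cohort 2 labs.** Protocol 5.4.3 says: "Table 4 displays the clinical laboratory parameters that must be measured at every visit". SAP 11.4.2 likewise has labs at all visits of the treatment period. Yet 5.3.3 lists only examination and vital signs, compliance and adverse events for Days 7, 14 and 21, and Table 5 has no blood volume for those days. The flow chart in 5.1 should settle this, but its hematology and biochemistry row is broken in this copy.

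**Liver criterion.** Protocol 7.2 makes a value of at least 2.0 × ULN in transaminases, alkaline phosphatase or total bilirubin a reason to stop treatment. It needs a measured value.

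**The concern.** The hold exists so that more subjects start 150 mg only once the first four have been watched for DLTs. If it can end after 2 weeks while the first scheduled safety lab comes at about 4 weeks, then an absence of laboratory DLTs at that moment partly means that nobody looked. Section 5.4.3 does not help Cohort 1, because a rule for every visit adds nothing where there is no visit.

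In Cohort 2 the three visits do take place, but a site can reasonably follow either text. Under one, the liver criterion can act with most of the dosing still to come. Under the other, dosing is practically over before a scheduled value exists.

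**Working it through.** **1. Does Table 5 hide a draw?** The tube volumes in Protocol 5.5 reproduce the Cohort 1 rows. Day 1 and Day 28 are each 8×12 + 5 + 3 + 10 + 3 + 50 = 167 mL, Day 35 is 12 + 5 + 3 + 10 + 3 = 33, and Day 56 is 33 + 50 = 83.

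- Cohort 1: 32.2 + 167 + 167 + 33 + 83 = 482.2 mL. With 2.7 mL for INR/PT at four visits it is 493.0 mL. Both equal the stated 482.2–493.0, so no draw falls between Day 1 and Day 28.
- Cohort 2: 19.2 + 124 + 132.5 + 20 + 48.5 = 344.2 mL, upper end 355.0, against a stated 345.2–354.0. The 1 mL slip at each end cannot hold three draws of 5 + 3 = 8 mL (24 mL). Table 5 therefore assumes no labs on Days 7, 14 and 21.

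**2. Who is measured when the hold ends?** Take the 2-week minimum, with the fourth subject on Day 15, and assume equal spacing g between starts. Subject k is then on study day 15 + g(4 − k) and is measured if that day has reached the lab visit V. Subject 4 is on Day 15 whatever g is, so is never measured. The spacing needed for the others is (V − 15)/3, (V − 15)/2 and (V − 15)/1:

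| Lab visit V | 1 of 4 measured | 2 of 4 | 3 of 4 |
|---|---|---|---|
| Day 26 | g ≥ 3.67 days | 5.5 | 11 |
| Day 28 | 4.33 | 6.5 | 13 |
| Day 30 | 5 | 7.5 | 15 |

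**3. Planned accrual.** The synopsis gives "Recruitment period: Q4 2016" to Q2 2018, without dates. The longest reading (1 Oct 2016 to 30 Jun 2018) is 638 days and the shortest (31 Dec 2016 to 1 Apr 2018) is 456. Divide by 36 subjects, with and without a 56-day pause for the Cohort 1 interim analysis:

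| Window | Days per subject | Subject 3 at the hold's end | Measured (V = 26 / 28 / 30) | Further starts before subject 4's lab |
|---|---|---|---|---|
| 638 | 17.7 | Day 32.7 | 3 / 3 / 3 | 11/17.7 = 0.6 to 15/17.7 = 0.8 |
| 638 − 56 | 16.2 | Day 31.2 | 3 / 3 / 3 | 0.7 to 0.9 |
| 456 | 12.7 | Day 27.7 | 3 / 2 / 2 | 0.9 to 1.2 |
| 456 − 56 | 11.1 | Day 26.1 | 3 / 2 / 2 | 11/11.1 = 1.0 to 15/11.1 = 1.4 |

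The wait from Day 15 to the fourth subject's lab is 26 − 15 = 11 to 30 − 15 = 15 days.

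**4. Liver criterion.** Doses left are 28 minus the visit day.

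- Cohort 1: 2 with a Day 26 visit and 0 at Day 28 or later.
- Cohort 2 under 5.3.3 and Table 5: the same 0 to 2.
- Cohort 2 under 5.4.3: 21, 14 and 7 after Days 7, 14 and 21, each ± 2.

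**The case against.** **The hold is not only a clock.** The DSMB reviews safety after every 4 patients recruited and may recommend stopping at any time (Protocol 3.1.3). Two weeks is a minimum, and 3.1.2 does not say the fifth subject starts on Day 15. The DSMB charter, which may say what the board must see, is not in this copy. This stands, and it rules out one tempting inference, that the DLT rule is inoperable. Day 28 labs still count, clinical DLTs and the subject diary remain, and significant unscheduled labs become adverse events (8.3.1). But a board can review only what was measured, and unscheduled labs depend on symptoms or initiative.

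**Cohort 2 has a safeguard.** It opens only after the Cohort 1 interim analysis, which includes hematology and biochemistry at three times the dose (3.1.1, 9.1.6). This is real mitigation, though those subjects are HIV-infected and on ART, while Cohort 2 is neither.

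**The every-visit wording may be boilerplate.** Protocol 5.4.2 puts ECGs at all visits, yet SAP 11.4.5 names four; SAP 11.4.2 mentions pregnancy tests in a males-only trial. So 5.4.3 may not express intent, and correcting it would also remove the conflict. A reader should not infer either that Cohort 2 certainly had no labs or that it certainly did.

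**Cohort 3 also waits until Day 28.** True, and at the same 50 mg. But its Day 28 and Day 56 labs leave 54–58 and 26–30 of 84 doses, so its liver criterion can act during dosing. It is not part of this point.

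**Prior data may justify a lab-free month.** They may. Sections 1.2.6 and 1.3 carry no text in this copy, so the documents support no judgement that the interval was unjustified.

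**Conclusion.** The point holds in this limited form. In Cohort 1, a hold released at its minimum leaves the fourth subject without a scheduled post-dose safety lab at any accrual speed. At planned average accrual 2 or 3 of 4 are measured, and about 0.6 to 1.4 further subjects could start 150 mg before the fourth subject's lab. Very fast accrual (starts 3 days apart or less) would leave none measured. The laboratory part of the rule is delayed by 11 to 15 days, not disabled.

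These figures assume equal spacing, release exactly at 2 weeks, and an average taken over all three cohorts; the actual Cohort 1 pace is not given. If DLTs are counted one per subject, laboratory DLTs alone can exceed 2 at release only with starts at least 11 days apart. If events are counted, one measured subject could suffice.

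In Cohort 2 there is an unresolved conflict between instructions. Its consequence is whether the liver criterion can first be triggered by a scheduled test with about 21 doses left or with 0 to 2. Both matters bear on participant safety and are cheap to mend, so they should be fixed.

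**What to change.** **(a) Cohort 1.** In Protocol 3.1.2, allow enrolment beyond the first four only after the DSMB has seen the Day 28 ± 2 hematology and biochemistry of all four. The cost is one sentence and 11 to 15 days, plus lab turnaround. This repairs the hold only; it gives the liver criterion no earlier value in Cohort 1. SAP 8 describes the Day 56 interim analysis as already produced. If Cohort 1 is complete, state in the report that no lab was scheduled between Day 1 and Day 28, so that an absence of laboratory DLTs at the hold is not read as measured and negative.

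**(b) Cohort 2.** If it is still open, resolve the conflict in favour of 5.4.3: add hematology and biochemistry to the Day 7, 14 and 21 visits in 5.3.3 and Table 5. The cost is an amendment and 3 × 8 = 24 mL per subject (24/345.2 = 7.0% more blood), at visits that already take place. SAP 3.3 speaks of this cohort as still to be enrolled, but that closely follows the protocol's wording and is weak evidence of trial status. If Cohort 2 is closed, correct 5.4.3 and SAP 11.4.2 to match what was done, and report it.
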